### **8.2.1. Inclusion criteria**

Patients must meet all of the following inclusion criteria to be eligible for inclusion in the study:

1. Patient  $\geq 18$  years diagnosed with COPD (any stage, the subgroups for the analysis would be based on COPD severity grade)

Redacted

2. Evidence of a personally signed and dated informed consent document indicating that the patient (or a legally acceptable representative) has been informed of all pertinent aspects of the study.
3. Ability to understand and complete the required QoL questionnaires
4. At least 2 years of clinical history available that includes records of previous moderate/severe exacerbations, influenza and pneumococcal vaccination history comorbidities and previous treatments.
5. Spirometry data\* (maximum 6 months old, or if not available at enrollment, to be performed as per normal clinical practice at visit 1 +/- one month)

\*Subjects with FEV1 <40 should be less than 20% of the total study population (related to the microbiological etiology dependent on severity)

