### **8.3. Variables**

**Variables to be recorded from previous clinical history and follow up visits (according to Table 1):**

- Consent date
- Subject code
- Demographic and epidemiological data;
- Antropometric data (weight, height, body mass index (BMI), Waist Circumference)
- Smoking habit, alcohol consumption
- Spirometric data (FEV1, FVC, FEV1/FVC)
- Pharmacological treatment
- COPD severity (GOLD)
  - o GRADE 1: Mild/unknown [FEV1≤ 80%, FEV1/FVC < 0,7 or no spirometry data]
  - o GRADE 2: Moderate [50% ≤ FEV1< 80%,FEV1/FVC < 0,7]
  - o GRADE 3: Severe [30% ≤ FEV1 < 50%, FEV1/FVC < 0,7]
  - o GRADE 4: Very severe [FEV1< 30% o FEV1< 50% plus respiratory failure,FEV1/FVC < 0,7]
- Number and severity of exacerbations

Redacted

- Frequency of total exacerbations (moderate and severe) in the previous year and during follow-up (recorded at hospital or primary care level).
- Comorbidities
  - o high blood pressure
  - o dyslipidemia
  - o type 2 diabetes mellitus
  - o metabolic syndrome
  - o heart failure
  - o ischemic heart disease
  - o chronic kidney disease
  - o cirrhosis
- History of neoplasia (solid organ and hematologic)
- Pneumococcal vaccination
- Influenza vaccination
- QoL questionnaire (reduced SGRQ, CAT) - completed by subjects and transcribed into electronic case report form (CRF)

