### **8.3.1 Study procedures**

#### **Visit 0: selection and recruitment**

- Obtain of signed informed consent document
- Confirmation of eligibility
- Assignment of subject number. Subject number will be assigned sequentially as the participants are included in the study. The number will be composed of 6 digits, first three will be the site code and last three the subject number.

Study authorized personnel will complete the case report form (CRF) for each of the subjects included. CRF (Annex 2) will be completed by an interview of the subject or review of clinical history and results of test/activities performed (as part of routine clinical practice)

Redacted

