5 ANALYSIS SYSTEMS / POPULATIONS

Considering that 37% of COPD patients will have one moderate/severe exacerbation per year, and assuming that at least 35% of patients will follow their doctor's vaccination

recommendation,³ to have at least 200 vaccinated COPD patients with moderate/severe exacerbations, a total of 1541 eligible subjects should be included in the analysis.

With 35% of patients vaccinated with PCV13, enrolling 1541 eligible subjects with COPD would provide approximately 540 patients in the PCV13 cohort and 1000 patients in the unexposed cohort.

Assuming that 37% of unexposed patients will present one moderate/severe exacerbation per year,² with 70% of the patients remaining in the study after 1 year, this sample size would provide 91% power to detect a statistically significant reduction of 10% in moderate/severe COPD exacerbations with PCV13 after 1 year. Assuming an additional 30% dropout in the second year, the study sample size would provide 91% power to detect a statistically significant reduction of 14% in moderate/severe COPD exacerbations with PCV13 after 2 years.

Time	PCV13		Unexposed		Power	Retention rate
	Sample size	% exacerbation	Sample size	% exacerbation		
Enrollment	540		1000			
1 year	378	27%	700	37%	91.43%	70% from enrollment
2 years	264	60%	490	74%	91%	70% from year 1

5.1 **FULL ANALYSIS**

The statistical analysis of this study will be carried out with all those evaluable patients with COPD, recruited by the Spanish sites participating in the study and who meet the following selection criteria:

5.1.1 **Inclusion Criteria**

Patients must meet all of the following inclusion criteria to be eligible for inclusion in the study:

1. *Aged 18 years or older at the time consent is given*
2. *Patient diagnosed with COPD (any stage, subgroups for analysis will be based on COPD severity)*
3. *Evidence of a personally signed and dated informed consent document indicating that the patient has been informed of all pertinent aspects of the study.*
4. *Ability to understand and complete the required quality of life questionnaires*
5. *Patients with at least 2 years of previous clinical history available relating to (if applicable) history of moderate/severe exacerbations, influenza and pneumococcal vaccination history, comorbidities and previous treatments*
6. *Spirometry data* (maximum 6 months old, or if not available at enrollment, to be performed as per normal clinical practice at visit 1 ± one month)*

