8.2.3 Effectiveness analysis

8.2.3.1 Study of exacerbations

A detailed analysis of the total number of exacerbations reported by the study patients will initially be performed. The absolute and relative frequency of patients who have reported at least two moderate exacerbations or one severe exacerbation per year (exacerbator patient) will be given.

The following indices will be calculated:

- NEPA (number of exacerbations patient/year) = Total no. of exacerbations reported by patients/ Patient follow-up time^{*)}
- NEPA Mild = Total no. of mild exacerbations/Patient follow-up time
- NEPA Moderate = Total no. of moderate exacerbations/Patient follow-up time
- NEPA Severe = Total no. of severe exacerbations/Patient follow-up time
- NEPA Moderate/severe = Total no. of moderate_severe exacerbations/Patient follow-up time

The following will also be calculated in the subpopulation of exposed patients:

- NEPA_pre_PCV13 = Total no. of exacerbations reported by the patient prior to receiving the PCV13 / Time to vaccination with PCV13^{**)}
- NEPA_pre_PCV13 (moderate/severe) = Total no. of moderate/severe exacerbations reported by the patient prior to receiving the PCV13 / Time to vaccination with PCV13^{**)*)}
- NEPA_post_PCV13 = Total no. of exacerbations reported by the patient after receiving the PCV13 / Time since vaccination with PCV13^{***)}
- NEPA_post_PCV13 (moderate/severe) = Total no. of moderate/severe exacerbations reported by the patient prior to receiving the PCV13 / Time since vaccination with PCV13^{***)}

*) Time from the date of COPD diagnosis to the date of the last follow-up visit. If the date of diagnosis of the disease is unknown, it will be computed as two years before the date of inclusion of the patient in the study

**) Time from date of COPD diagnosis to date of PCV13 vaccination

***) Time from vaccination with PCV13 to date of the last follow-up

Each of the indices calculated above will be described using the main measures of central tendency and dispersion (mean, median, standard deviation, confidence intervals, minimum, maximum and interquartile range).

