The Student's t test, one-way ANOVA or its non-parametric equivalents, the Mann-Mann U test or Kruskal-Wallis H test will be used to determine if statistically significant differences are observed in NEPA, NEPA Mild, NEPA Moderate, NEPA Severe and NEPA Moderate/Severe according to the severity of COPD and type of patient (exposed/unexposed). In order to determine the impact of PCV13 vaccination on exacerbations, paired data comparisons will be made between (NEPA_pre_PCV13 vs. NEPA_post_PCV13) and (NEPA_pre_PCV13 (moderate/severe) vs. NEPA_post_PCV13 (moderate/severe)), using the Student's t-test for paired data or its non-parametric equivalent, the Wilcoxon test.

In order to study which subgroups of patients obtain a greater benefit from vaccination

with PCV13 according to COPD severity, paired data comparisons will be made between (NEPA_pre_PCV13 vs. NEPA_post_PCV13) and (NEPA_pre_PCV13 (moderate/severe) vs. NEPA_post_PCV13 (moderate/severe)), in each of the four patient subpopulations established based on disease severity.

In order to determine the factors associated with the presence of an exacerbator patient, a logistic regression model will be constructed, whose dependent variable is (exacerbator/non-exacerbator patient) and, as independent variables, all those possible factors that have been significant in the univariate models ($p_{value} < 0.25$), following the methodology of Hosmer-Lemeshow.

- ❖ Vaccine exposure (PCV13 yes/no)
- ❖ COPD severity (Grade I, Grade II, Grade III, Grade IV)
- ❖ Age
- ❖ Sex
- ❖ Time since diagnosis of the disease
- ❖ Patient with stable treatment for at least three months
- ❖

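### The all-severity before/after PCV13 test counts mild exacerbations that the history need not contain, so poorer capture before inclusion could hide a benefit

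*SAP*

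**What the plan says.** SAP 8.2.3.1 defines the pre-vaccination rate as "NEPA_pre_PCV13 = Total no. of exacerbations reported by the patient prior to receiving the PCV13" over the time from COPD diagnosis to vaccination. The post-vaccination rate uses "Total no. of exacerbations reported by the patient after receiving the PCV13" over the time since vaccination. Neither numerator has a severity limit. Mild events belong to the count: the definitions under Protocol Table 1 include exacerbations treated with a new bronchodilator alone, and the SAP gives them their own index, "NEPA Mild = Total no. of mild exacerbations/Patient follow-up time".

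The stated use is causal: "In order to determine the impact of PCV13 vaccination on exacerbations, paired data comparisons will be made". The all-severity pair and a moderate/severe pair are both tested this way, in all exposed patients and again within each of the four GOLD grades.

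For the time before inclusion, Protocol 8.2.1 requires "At least 2 years of clinical history available that includes records of previous moderate/severe exacerbations". SAP 5.1.1 likewise asks for "history of moderate/severe exacerbations, influenza and pneumococcal vaccination history, comorbidities and previous treatments". Protocol 8.7 and SAP 8.2.1 repeat the same scope. After inclusion, Protocol Table 1 schedules a question on exacerbations at months 1, 6, 12, 18 and 24, with telephone contact at months 6 and 18 where applicable.

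**The concern.** The all-severity test compares two periods in a category of event that need be on file for only one of them. A patient can meet the history requirement with no mild event ever abstracted, and then have mild events recorded at up to five follow-up contacts. The post-vaccination rate would rise with no change in the disease.

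A real reduction could then shrink, vanish or look like an increase. The second primary objective, which asks which GOLD grade benefits most, would be exposed too, because the same pair is tested grade by grade and mild events may be more common in some grades than in others.

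The moderate/severe pair does not give cover as printed. The numerator of its post-vaccination index counts events before vaccination, so it repeats the pre-vaccination count over a different denominator.

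**Working it through.** **Planning inputs.** Protocol 8.5 and SAP 5 give one-year risks of a moderate/severe exacerbation of 37% (control, n = 700) and 27% (PCV13, n = 378), with a stated power of 91.43%. SAP 4 sets p < 0.05; I take it as two-sided.

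**Reproducing the plan's figure.**
- Pooled proportion: (378×0.27 + 700×0.37)/1078 = 0.335.
- Standard error under the null: √[0.335×0.665×(1/378 + 1/700)] = 0.0301.
- Standard error under the alternative: √[0.27×0.73/378 + 0.37×0.63/700] = 0.0292.
- Power: Φ[(0.10 − 1.96×0.0301)/0.0292] = 91.9%, or 90.8% with a continuity correction. The inputs are therefore read as intended.

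**From risks to rates.** The 37% and 27% are proportions of patients, while NEPA is a rate of events. Under a Poisson model the rates are −ln(0.63) = 0.462 and −ln(0.73) = 0.315 per patient-year, a ratio of 0.68. I use this between-group planning effect as the true before/after effect.

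**Effect of unequal capture.** Let m be the mild share of all true exacerbations and c the share of mild events found in the history. Assume vaccination at inclusion, full capture afterwards, and the same vaccine effect on mild events. Then

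observed ratio = 0.681 / [(1 − m) + c·m].

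| Mild share m | c = 0 | c = 0.5 | c = 1 |
|---|---|---|---|
| 20% | 0.681/0.80 = 0.85 | 0.681/0.90 = 0.76 | 0.68 |
| 30% | 0.681/0.70 = 0.97 | 0.681/0.85 = 0.80 | 0.68 |
| 40% | 0.681/0.60 = 1.14 | 0.681/0.80 = 0.85 | 0.68 |

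With c = 0 the benefit disappears when m = 1 − 0.681 = 32%, a mild rate of 0.462×(1/0.681 − 1) = 0.22 per patient-year. If the vaccine has no effect on mild events, the break-even rate is 0.462×(1 − 0.681) = 0.15, a share of 0.147/(0.462 + 0.147) = 24%.

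**Effect on the test.** The paired t-test was simulated with 264 vaccinated patients (the plan's two-year figure), two years before and two after, an assumed gamma frailty variance of 1, and 2,000 runs per scenario.
- Moderate/severe events only: significant benefit in about 96–97% of runs.
- Mild rate 0.2 per patient-year (a share of 0.2/0.662 = 30%), none in the history: ratio 0.98, benefit in 4.5% of runs.
- Same mild rate, half in the history: ratio 0.81, benefit in 69%.
- Mild rate 0.3, none in the history: ratio 1.12, benefit in 0.1%, significant apparent harm in 24%.

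**Direction.** Protocol 8.2 allows vaccination before or after inclusion. If before, all pre-vaccination time is history and post-vaccination time is part history, part follow-up. If after, pre-vaccination time is part history, part follow-up and all post-vaccination time is follow-up. In neither case is the post period covered less well than the pre period. Timing changes the size of the capture bias, not its sign.

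**The case against.** The strongest reply is that an entry criterion sets a minimum and does not limit what is abstracted. Protocol 8.3 lists the number and severity of exacerbations for both history and follow-up. A mild event requires a new prescription, which should leave a trace. Protocol 8.2 says that earlier data are available to the same standard as prospective data. All of this is fair, and it means that unequal capture is possible rather than certain. It does not close the gap: the statement on standards is general and does not mention mild events, and no rule sets the severity scope or source for each period.

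A reader might infer that the plan prescribes records for the history and interview for follow-up. It does not. The sentence that the CRF "will be completed by an interview of the subject or review of clinical history" stands under Visit 0, so interview is open for the history as well. The protocol's own frequency variable, "Frequency of total exacerbations (moderate and severe) in the previous year and during follow-up (recorded at hospital or primary care level", has one scope and one source for both periods.

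A reader might also infer that the bias favours the vaccine in some patients. On timing alone it cannot, as shown above. Nor do the documents show that exposed and unexposed patients differ in capture, so the point does not carry over to that comparison.

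Finally, the primary objective concerns moderate/severe events, and the SAP already tests that pair alongside. This limits the harm, but only once the pair's post-vaccination numerator is corrected.

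**Conclusion.** The point holds in conditional form. The SAP offers the all-severity pair as evidence of impact without securing equal capture of mild events on the two sides. If capture is poorer before inclusion, the comparison is biased toward no benefit, by an amount that depends on the mild share, the capture rate and the timing of vaccination.

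The figures are illustrations. With no mild events in the history, a true ratio of 0.68 appears as 0.85 to 1.14 over mild shares of 20% to 40%; with half captured, as 0.76 to 0.85. Zero capture is the extreme case. Dividing the two planning risks directly (0.27/0.37 = 0.73) would suggest an apparent increase already at a 30% mild share (0.73/0.70 = 1.04). That treats patient proportions as event rates; on the rate scale the figure is 0.97.

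The conclusion concerns capture only. Regression to the mean could push the other way. A pre-vaccination denominator that starts at diagnosis, when only two years of history are required, could push the same way.

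**What to change.** In SAP 8.2.3.1:

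- Base the before/after impact test, overall and by GOLD grade, on moderate/severe exacerbations only, taken from hospital or primary-care records in both periods.
- Limit pre-vaccination time to the documented history instead of starting it at COPD diagnosis.
- Correct the numerator of the moderate/severe post-vaccination index so that it counts events after vaccination. Without this the retained test cannot be used.
- Remove the all-severity pair as evidence of impact. Report NEPA Mild and all-severity NEPA descriptively, for inclusion to last visit only.

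This matches the primary objective and the protocol's own frequency variable, and it needs only SAP wording. The cost is that events known only from interview drop out of the before/after test.

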## **Study procedures**

Subjects identified with COPD will be informed about the study and invited to participate by investigators at the time of their routine control visits. All therapies will be prescribed according to the updated National COPD Guidelines (GesEPOC) indicating among other therapies active reduction of risk factors, influenza and pneumococcal vaccination (with PCV13) in all patients with mild, moderate or severe COPD. All the patients will be counselled to stop smoking and advised on life-style modifications. Any vaccination will be prescribed according to clinical practice and not related to the decision to include the subjects in the study. Subjects may be vaccinated before or after inclusion in the study.

Study will include periodic scheduled visits for all patients, to complete a total follow up of 2 years (see Table 1).

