## **8.7. Data analysis**

Depending on recruitment and data availability an interim analysis may be performed after the first year, if at least 75% of subjects included have completed one year of follow up.

- To determine the impact of PCV13 vaccination, the incidence of exacerbations will be determined 2 years after the inclusion in the study and will be compared with the incidence 2 years before the study (2 years of clinical history required including records of previous moderate/severe exacerbations, influenza and pneumococcal vaccination history comorbidities and previous treatments)
- A descriptive analysis of all variables will be performed. Qualitative variables will be analyzed by absolute and relative frequencies. Quantitative variables will be studied by the usual centralization and dispersion measures (mean, median, standard deviation, confidence intervals, minimum, maximum and interquartile range).
- For comparison of independent samples, the Pearson chi-squared test or the exact Fisher test for 2x2 tables or likelihood ratio for mXn tables, for qualitative variables, will be used. The Student's t test, one-way ANOVA or its non-parametric equivalent U-Mann-Mann, H-Kruskal-Wallis for quantitative variables will be used.
- For comparison of paired samples, the McNemar's test will be used for qualitative variables and Student's t test or Wilcoxon's test for quantitative variables.
- A multivariate logistic regression analysis will be performed, in order to identify risk factors associated with exacerbations. Exacerbations existence (yes/no) will be used as dependent variable. Vaccination with PCV13 and statistically significant variables in the univariate model, will be used as possible risk factors: demographic characteristics, influenza vaccination, smoking habit, etc. In addition, potential confounding variables will be considered: phenotype, comorbidities, COPD severity, FEV1 (no control possible based on the study design)
- Appropriate tests will be performed accordingly to determine if the necessary requirements are fulfilled for the use of parametric contrasts.
- Estimates will be performed with a 95% confidence interval. The SPSS statistical package version 19.0 or later will be used.

Redacted

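### The SAP's post-vaccination moderate/severe exacerbation rate counts events from before vaccination, so its paired before/after test contains no post-vaccination event

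*SAP*

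**What the plan says.** SAP 8.2.3.1 defines four before/after indices for exposed patients. Three are coherent. The moderate/severe pre-vaccination rate is "NEPA_pre_PCV13 (moderate/severe) = Total no. of moderate/severe exacerbations reported by the patient prior to receiving the PCV13 / Time to vaccination with PCV13", and the all-severity post-vaccination rate is "NEPA_post_PCV13 = Total no. of exacerbations reported by the patient after receiving the PCV13 / Time since vaccination with PCV13". The fourth reads "NEPA_post_PCV13 (moderate/severe) = Total no. of moderate/severe exacerbations reported by the patient prior to receiving the PCV13 / Time since vaccination with PCV13".

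The footnotes run the pre-vaccination period from COPD diagnosis to PCV13, and the post-vaccination period from PCV13 to the last follow-up. For the overall index, a missing diagnosis date has a fallback: "If the date of diagnosis of the disease is unknown, it will be computed as two years before the date of inclusion".

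The section then states the use of these indices: "In order to determine the impact of PCV13 vaccination on exacerbations, paired data comparisons will be made between" the pre and post rates, once for all exacerbations and once for moderate/severe ones, by paired t-test or Wilcoxon test. To find which patients benefit most, the same comparisons are repeated "in each of the four patient subpopulations established based on disease severity". SAP 2.2 names moderate/severe exacerbations as the outcome of the first primary objective and benefit by COPD severity as the second.

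**The concern.** The index called post-vaccination takes its events from before vaccination and divides them by time after vaccination. Its numerator matches the pre-vaccination index word for word. The moderate/severe paired comparison would therefore set one event count against itself over two different durations, and exacerbations after PCV13 would not enter.

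The formula runs and returns ordinary-looking rates, so the error need not show itself in the output. Protocol 8.2 (Study procedures) allows for varied timing: "Subjects may be vaccinated before or after inclusion in the study". The two periods will therefore often differ in length, and the longer one sets the direction of the result. Across GOLD grades, the apparent differences would come from pre-vaccination counts, time since diagnosis and timing of vaccination rather than from benefit. The descriptive tables that the SAP requires for each index would be wrong too.

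**Working it through.** The documents give no figure that depends on this definition, so there is none to reproduce. The check is algebra on the SAP's formulas, followed by an illustration.

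**Algebra (no assumptions).** Let E_pre be a patient's moderate/severe events before PCV13, T_pre the time from diagnosis to PCV13, and T_post the time from PCV13 to last follow-up.

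- Pre rate = E_pre / T_pre.
- Post rate as written = E_pre / T_post.
- Post/pre = T_pre / T_post when E_pre > 0.
- Post − pre = E_pre × (1/T_post − 1/T_pre).
- When E_pre = 0 both rates are 0, however many events follow vaccination.

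No term depends on an event after vaccination.

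**Size of the distortion.** Assume diagnosis D years before inclusion, 24 months of follow-up, and vaccination at month m from inclusion (negative means before). Then T_pre = D + m/12 and T_post = 2 − m/12. D = 2 is the SAP's fallback, assumed to apply to the pre-vaccination period as well. D = 10 is an assumption that shows a longer disease history.

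| Vaccination | Ratio, D = 2 | Ratio, D = 10 |
|---|---|---|
| 12 months before inclusion | 1/3 = 0.33 | 9/3 = 3.0 |
| At inclusion | 2/2 = 1.00 | 10/2 = 5.0 |
| Month 6 | 2.5/1.5 = 1.67 | 10.5/1.5 = 7.0 |
| Month 12 | 3/1 = 3.00 | 11/1 = 11.0 |

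**What the paired test would show.** Inputs: n = 264 vaccinated patients at 2 years (SAP 5, size table), and 0.37 events per patient-year (the 37% per year in SAP 5, used as a rate). Poisson counts, D = 2 and one common vaccination month are assumptions.

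Each difference is E_pre times a constant, so the constant cancels and |t| ≈ √(n × 0.37 × T_pre):

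- 12 months before inclusion: √(264 × 0.37 × 1) = 9.9. The rate falls from 0.37 to 0.12 (0.37 × 1/3), a false benefit.
- At inclusion: every difference is 0 and the test cannot be computed.
- Month 6: √(264 × 0.37 × 2.5) = 15.6. The rate rises from 0.37 to 0.62 (0.37 × 2.5/1.5), a false harm.
- Month 12: √(264 × 0.37 × 3) = 17.1. The rate rises from 0.37 to 1.11 (0.37 × 3), a false harm.

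These values are the same whether the true reduction is 0%, 50% or 100%.

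**With the numerator corrected (month 6).** The mean difference is −0.37r for a true reduction r. Its variance per patient is 0.37(1 − r)/1.5 + 0.37/2.5.

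- r = 0: mean difference 0, t ≈ 0.
- r = 0.5: mean −0.185; variance 0.123 + 0.148 = 0.271; SE = √(0.271/264) = 0.032; t ≈ −5.8.
- r = 1: mean −0.37; variance 0.148; SE = √(0.148/264) = 0.0237; t ≈ −15.6.

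The corrected index responds to the vaccine; the written one does not. Simulation with these inputs gave the same t values to within about 0.1.

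**The case against.** The strongest reply is that the slip reveals itself. The index name, its denominator and the all-severity definition one line above all point to events after vaccination. SAP 8.2.3.6 describes the parallel cost analysis as before versus after vaccination. A competent programmer would probably notice. That is fair, and it is why the error looks clerical. But the program would then depart from the written SAP on the outcome of the first primary objective, and a correction made after results are known is open to challenge.

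Second, the study was sized for vaccinated versus unexposed patients, and that comparison is untouched. This stands as a limit on scope. The SAP does not label the paired test primary. It does, however, assign both the impact question and the by-grade question to the paired tests.

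Third, the illustration is narrow. The fallback diagnosis date applies only when the date is unknown. With vaccination 12 months before inclusion, the ratio exceeds 1 once diagnosis is more than 4 years before inclusion, since T_pre = D − 1 then exceeds T_post = 3. The false-benefit example therefore depends on a short disease history. Also, 37% is a proportion of unexposed patients. Converted to a Poisson rate it is −ln(0.63) = 0.462, which moves the month-6 t to √(264 × 0.462 × 2.5) = 17.5. These points change the illustrative sizes but leave the algebra intact.

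Fourth, protocol 8.7 is only partial support for the intended reading. It says "the incidence of exacerbations will be determined 2 years after the inclusion in the study and will be compared with the incidence" in the 2 years before the study, so it is anchored on inclusion rather than vaccination. It does confirm that an after-versus-before contrast is meant.

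**Conclusion.** The concern holds and should be corrected before analysis. As written, the moderate/severe post-vaccination rate contains no post-vaccination event, and its ratio to the pre-vaccination rate is T_pre/T_post for every patient with an earlier event. That conclusion needs no assumptions. The ratios of 0.33 to 3.00 rest on the fallback diagnosis date, 24 months of follow-up and assumed vaccination months. The t values also rest on Poisson counts, a rate of 0.37 per year and one common vaccination month.

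The damage is confined to the moderate/severe before/after comparison, its repeats in the four GOLD grades, and the descriptive summaries of this index. The all-severity pair, the exposed/unexposed comparisons and the logistic models are not affected by this error.

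**What to change.** In SAP 8.2.3.1, change the numerator of the post-vaccination moderate/severe index from events *prior to* PCV13 to events *after* it. Confirm that the analysis program counts post-vaccination events for that index. The cost is one phrase and one program check, with no new data.

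A separate matter can be settled in the same revision. The definitions under Table 1 in protocol 8.3.1 treat a patient with an exacerbation as vaccinated only from 15 days after immunization, whereas the SAP footnotes split time at the vaccination date itself. Reconcile the four before/after indices and their two footnotes with that definition, and state how events and time in days 0 to 14 are handled. This is also a text change only.

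### SAP 8.2.3.1: exacerbation rates (NEPA) use person-time from COPD diagnosis with no matching event window, are not split at vaccination between cohorts, and contain a numerator slip

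*SAP*

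**What the plan says.** SAP 8.2.3.1 defines NEPA as exacerbations per patient-year. The denominators are:

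- Overall NEPA, all severities and by severity: "Time from the date of COPD diagnosis to the date of the last follow-up visit". If the diagnosis date is unknown, "it will be computed as two years before the date of inclusion of the patient in the study".
- NEPA_pre_PCV13: "Time from date of COPD diagnosis to date of PCV13 vaccination".
- NEPA_post_PCV13: from vaccination to last follow-up.

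The footnote marker on NEPA_pre_PCV13 (moderate/severe) combines two symbols, so it is unclear whether the fallback also applies there. The all-severity post index is "Total no. of exacerbations reported by the patient after receiving the PCV13 / Time since vaccination with PCV13". The moderate/severe post index is "Total no. of moderate/severe exacerbations reported by the patient prior to receiving the PCV13 / Time since vaccination with PCV13".

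The section then says: "In order to determine the impact of PCV13 vaccination on exacerbations, paired data comparisons will be made" between the pre and post indices. It repeats them within each GOLD grade: "In order to study which subgroups of patients obtain a greater benefit from vaccination". Overall NEPA is compared between exposed and unexposed patients.

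On history, SAP 5.1.1 requires "Patients with at least 2 years of previous clinical history available", covering moderate/severe exacerbations; Protocol 8.2.1 agrees. Protocol 8.7 compares the two years after inclusion with the two years before. Protocol 8.3 lists exacerbation frequency for the previous year (and, separately, number and severity with no time limit). SAP 6 speaks of previous years.

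**The concern.** A rate needs its events and its time at risk drawn from the same period. Here the time starts at diagnosis, while the documents assure events only from two years before inclusion and do not say from when events are counted.

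The indices carry the vaccine-impact comparison. The paired comparison by grade is the only analysis that the SAP ties to the second primary objective. If grades differ in disease duration, a bias that depends on duration can look like a difference in benefit. The cohort comparison has a separate problem: Protocol 8.2 allows vaccination before or after inclusion, yet a vaccinated patient's whole record since diagnosis counts as exposed.

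**Working it through.** The documents state no NEPA figure, so there is none to reproduce.

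**Inputs.** D is years from diagnosis to inclusion and m is years from inclusion to vaccination. Follow-up is 2 years and assured history is 2 years before inclusion. The documents do not give D. I take D of at least 2, because SAP 8.2.1 excludes more recent diagnoses if its wording is read as before inclusion. A true rate ratio (RR) of 0.70 is illustrative. The one-year planning proportions (37% and 27%, Protocol 8.5) imply RR = ln(0.73)/ln(0.63) = 0.68 with Poisson counts (0.462 events/year). With gamma frailty of shape 1, which is my assumption, RR = (0.27/0.73)/(0.37/0.63) = 0.63 (0.587 events/year).

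**1. No split at vaccination.** With equal D and a two-year record, the exposed/unexposed ratio of overall NEPA is [(2+m) + RR(2−m)]/4.
- m = 0: (2 + 1.40)/4 = 0.85.
- m = 1: (3 + 0.70)/4 = 0.925.

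With unequal D the error can go either way. With no vaccine effect, exposed D = 10, unexposed D = 5 and a two-year record, the ratio is (4/12)/(4/7) = 0.58.

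**2. Fallback.** For D = 8 and 2 years of follow-up, the denominator is 8 + 2 = 10 years if the date is known and 2 + 2 = 4 years if not. The same events give a 2.5-fold difference in NEPA.

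**3. Numerator.** Programmed literally, NEPA_post (moderate/severe) contains no post-vaccination event. Take 0.37 events/year for illustration and a two-year record. At m = 0 it equals 0.37 × 2/2 = 0.37 whatever the vaccine does. At m = 1 and D = 2 it is 0.37 × 3/1 = 1.11, against a pre rate of 0.37 × 3/3 = 0.37.

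**4. Unmatched pre-vaccination window (conditional).** If only the assured two years are captured, the expected post/pre ratio is RR × (D+m)/(2+m). At m = 0 and RR = 0.70:
- D = 2 gives 0.70, D = 4 gives 1.40, D = 8 gives 2.80.
- The ratio passes 1 at D = 2/0.70 = 2.86 years (2.94 for RR 0.68, 3.18 for 0.63).
- Two grades with the same true RR of 0.63 but assumed D of 3 and 8 read 0.63 × 3/2 = 0.94 and 0.63 × 8/2 = 2.52.

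If a share c of the earlier events is captured, the ratio at m = 0 becomes RR × D/[2 + c(D−2)]. For RR 0.70 and D = 8 this is 0.70 × 8/3.5 = 1.60 at c = 0.25, 0.70 × 8/5 = 1.12 at c = 0.5, and 0.70 at c = 1.

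**5. Effect on the paired test.** I simulated 264 vaccinated patients (the year-2 row of the study-size table), m uniform on 0 to 1, a constant rate, the one-year planning rates and two-sided 0.05. Entries are the percentage of runs that are significant, t-test / Wilcoxon.

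| D (years), capture | Frailty, RR 0.63 | Poisson, RR 0.68 |
|---|---|---|
| 2–8, two years only | 49 / 30 worse, 0 better | 70 / 51 worse |
| 2–8, 25% of earlier events | about 2 / under 1 worse | about 10 / 3.5 worse |
| 2–8, 50% of earlier events | 52 / 73 better | 18 / 41 better |
| 2–4, two years only | 0 worse, 34 / 46 better | 0 worse, 11 / 20 better |
| Matched window | nearly 100 better | 96 / 97 better |

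Complete capture at a constant rate also gives nearly 100% better under frailty. Monte Carlo error is about 1 percentage point, and repeat runs agreed closely.

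The two-year planning proportions (60% and 74%) with the same frailty imply 0.74/0.26/2 = 1.42 events/year and RR = (0.60/0.40)/(0.74/0.26) = 0.53. With D 2–8 and two-year capture, significantly worse results then fall to about 6–8% / 3–4%. Under Poisson they rise to about 85% / 68%.

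**The case against.** The strongest reply is that no mismatch in NEPA_pre is proven. The SAP sets no numerator window, so the event count can be read as running back to diagnosis, in step with the denominator. Two years is an eligibility floor and not a limit on data capture, and Protocol 8.2 and SAP 6 both point to earlier years being available. The CRF (Annex 2) would settle it, but its content is not in the documents. This stands: the wording shows an undefined window, and the bias in item 4 is conditional. It is not a full rescue, because SAP 2 notes that exacerbation frequency rises as the disease advances. Early years would therefore lower the pre-vaccination rate even with complete capture, again against the vaccine.

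A reader might infer that the planned test will make a useful vaccine look harmful. The documents do not support that. A significant reversal needs almost no capture of earlier events together with long disease, and its frequency depends heavily on assumed rates and on D. Capture of a quarter of earlier events nearly removes it under frailty and makes it uncommon under Poisson, although power is then mostly lost.

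A reader might also infer from the literal numerator that pre-vaccination events are meant to be counted after vaccination. The line for all exacerbations shows otherwise.

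None of this answers items 1 and 2, which do not depend on how far back events are captured.

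**Conclusion.** This must be corrected before analysis. The missing split, the inconsistent fallback with its unclear marker, and the numerator slip are certain from the text. The dilution from 0.70 to 0.85 or 0.93 assumes equal disease duration and a two-year record; the existence of the misclassification does not.

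The NEPA_pre bias rests on an unknown capture period and unknown D. It ranges from little harm (complete capture at a constant rate), through lost power (partial capture), to a reversed sign as the worst case. Patients vaccinated before inclusion were not simulated. Their assured pre-vaccination period is under two years, and is nil if vaccination was more than two years before inclusion.

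The SAP 8.1 logistic model of exacerbations during the study and the sample size are not affected. That model specifies no vaccine-by-grade analysis, however, so it does not stand in for the paired comparison by grade.

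**What to change.** Check on the CRF how far back exacerbations are recorded and whether they carry onset dates. Then amend SAP 8.2.3.1:

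- Count events and person-time over one window consistent with Protocol 8.7: from 24 months before inclusion, or the start of dated capture if later, to last follow-up. Split it at PCV13 using the protocol's 15-day definition of vaccinated status.
- Drop the diagnosis date and its fallback from the denominators, and correct the footnote markers.
- Correct the NEPA_post (moderate/severe) numerator to events after PCV13.
- Make moderate/severe the main paired comparison. Mild events have no assured history, so limit comparisons that include them to periods in which they are recorded.
- For exposed against unexposed, use time after inclusion, count vaccinated patients' earlier time as unexposed, and adjust for the confounders named in SAP 8.1. A rate model with a person-time offset is one option.
- State the same time base for the exacerbator outcome, whose per-year criterion has none.

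The cost is mainly SAP wording and programming. Patients vaccinated before the window leave the paired test, so set a minimum pre-period and report exclusions, since short pre-periods give unstable rates. Protocol 8.7 says that major changes to primary analyses go into a protocol amendment, so one may be needed.
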